- No medications, supplements which can affect PSA within 30 days prior to informed consent including toremifene citrate, finasteride, testosterone, dehydroepiandrosterone (DHEA) or other testosterone-like supplements. No dutasteride within 90 days of first noni dose.
- No baseline PT/PTT abnormalities, coagulopathies or anticoagulant drug use, such as heparin, or warfarin (Coumadin)
- Consumption of any concomitant nutritional, herbal supplements, and antioxidants should be taken under the discretion of the investigator.
- No current use of Noni or noni-containing products

Initial Laboratory/Radiologic Results must be within normal range for age:

- Complete blood count (CBC \overline{c} diff)
- Complete metabolic profile including liver function tests (CMP + LFT)
- PT/PTT
- MRI of the pelvis with contrast
- Very low or low risk classification confirmed by Oncotype DX Prostate Test.

SCHEMA

Screening/Pre-Enrollment:

Baseline/Enrollment:

Intervention:

Self-administration of Noni capsules

6,000 mg/day in divided doses x 12 months

with

Clinic Visits at Months 1, 3, 6, 9

End of Intervention: (Month 12)

Post-intervention Follow-up: (7+- 3 days post-treatment)

Page 4 of 38

CONFIDENTIAL

Sample size:

The estimated sample size is a total of 30 subjects with paired biopsies (initial diagnosis and 12 months)

Endpoints:

Efficacy (Primary):

- Induction of favorable gene expression changes on Oncotype Dx Prostate Cancer Test after 12 months of intervention with Noni extract (6,000 mg daily)
- Incidence of tumor progression after 12 months of intervention with Noni extract
- Serum PSA doubling time

Safety:

- Primary: Incidence and severity of AEs
- Secondary: Effects on angiogenesis (CD34), cell proliferation (Ki-67) and apoptosis (TUNEL) in prostate tissue biopsy samples from month 12

Version Date: 11/09/15

Table of Contents

OBJECTIVES	9
Primary	9
SECONDARY	9
BACKGROUND	9
DISEASE BACKGROUND	9
STUDY DRUG	10
NONI EXTRACT	10
CLINICAL EXPERIENCE: NONI EXTRACTS AND CANCER	11
PATIENT ENROLLMENT CRITERIA	11
INCLUSION CRITERIA	11
EXCLUSION CRITERIA	12
INCLUSION OF WOMEN AND MINORITIES	13
RECRUITMENT PLAN	13
TREATMENT PLAN	13
DOSE REGIMEN AND DOSE GROUPS	13
CONTRAINDICATIONS	14
CONCOMITANT MEDICATIONS	14
DOSE MODIFICATIONS	14
RULES FOR DOSE SUSPENSION AND DISCONTINUATION	16
REPLACEMENT	17
ADHERENCE/COMPLIANCE	17
PHARMACEUTICAL INFORMATION	17
Noni	17
RATIONALE FOR DOSE SELECTION AND ADMINISTRATION	18
AVAILABILITY	18
DRUG ACCOUNTABILITY	18

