PATIENT ENROLLMENT CRITERIA

The criteria for inclusion or exclusion of study participants.

Inclusion Criteria

- 1. Men with a diagnosis of very low risk (<5% risk of disease relapse after primary treatment, criteria; cT1c, Gleason ≤6, PSA < 10 ng/mL, fewer than 3 positive biopsy cores ≤ 50% cancer in any core, PSA density < 0.15 ng/mL/g); low risk (10% risk of disease relapse after primary treatment, criteria; cT1-2a, Gleason ≤6, PSA < 10 ng/mL) prostate cancer
- 2. Very low risk and low risk groups will be confirmed by Oncotype DX prostate cancer test and provided a Genomic Prostate Score (GPS)
- 3. 55 years of age and older (\geq 55 years) at the time of informed consent

- 4. No evidence of extraprostatic disease on pelvic MRI
- 5. No baseline PT/PTT abnormalities, coagulopathies, or who are on any blood thinners.
- 6. ECOG performance status 0-2 (Appendix A)
- 7. Participants must have normal organ and marrow function as demonstrated by the following parameters being:
 - a. complete blood count with differential (CBC \overline{c} diff) no clinically significant findings
 - b. complete metabolic profile (CMP) no clinically significant findings
- 8. Willing to comply with proposed visit and treatment schedule
- 9. Able to understand and willing to sign a written informed consent document

Exclusion Criteria

- 1. Prior history of treated prostate cancer
- 2. Concomitant use of medications that are known CYP3A4 substrates
- 3. Use of medications or supplements that are known to affect PSA within 30 days prior to informed consent, including toremifene citrate, finasteride, testosterone, dehydroepiandrosterone (DHEA) or other testosterone-like supplements. No dutasteride within 90 days prior to first noni dose (**Appendix B**)
- 4. Consumption of any concomitant nutritional, herbal supplements, and antioxidants should be taken under the discretion of the investigator. The following foods/supplements are prohibited at least 7 days prior to initiation of and during study treatment:
 - St. John's wort or hyperforin (potent CYP3A4 enzyme inducer)
 - Grapefruit juice (potent cytochrome P450 CYP3A4 enzyme inhibitor)
- 5. Use of any blood thinners.
- 6. Consumption or use of any Noni or Noni-containing products
- 7. History of renal or hepatic disease, including history of hepatitis B or C. Uncontrolled intercurrent illness including, but not limited to, ongoing or active infection, symptomatic congestive heart failure, unstable angina pectoris, cardiac

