Procedures that will be performed as part of the screening/pre-enrollment process are described below.

- Very low risk or low risk prostate cancer must be present in at least one of 8 cores from the diagnostic biopsy. Representative slides and biopsy paraffin blocks from the initial biopsy are required for Oncotype DX analysis (mandatory) and review by pathologists affiliated with the UHCC consortium.
- All subjects will have the study fully explained to them and will sign an informed consent document prior to having any invasive procedures performed.
- A limited physical exam will be performed, including anthropometric measurements (height and weight) and vital signs (blood pressure).
- Epidemiological Data: The research staff will obtain personal and physical characteristics, family history, history of environmental and personal exposures, alcohol intake, dietary and physical activity, cancer screening, medication use including nutritional supplements and disease outcomes as detailed in the Excel workbook CRF.
- Pelvic MRI with contrast will be performed to ensure there is no extraprostatic disease. (Please note, MRI is not required at the screening visit if results are available from testing performed within twelve months of enrollment.)
- Blood will be drawn for serum PSA, CMP, PT/PTT and CBCc diff. (*Please note, measurement of PSA is not required at the screening visit if results are available from testing performed prior to the diagnostic biopsy, and within three months of enrollment.*)
- A DRE will be performed. (Please note, this test is not required at the screening visit if performed by participating study sub-investigator within six months of enrollment.)

Enrollment

Procedures followed during the enrollment visit are described below. Enrollment should take place within 4 weeks of the screening visit.

- All components of eligibility will be confirmed (inclusion criteria, exclusion criteria).
- Results from PSA, CMP, PT/PTT and CBC \overline{c} diff tests should be available prior to enrollment.
- Subjects will be interviewed for baseline symptoms and concomitant medications.
- LUTS score will be assessed using the AUA BPH Symptom Score Questionnaire (**Appendix D**).
- Subjects will complete the UCLA QoL questionnaire (Appendix E).
- Blood will be collected for baseline scopoletin measurement and banking.

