- The research staff will collect the investigational agent intake log, review signs and symptoms, and concomitant medications. All symptoms and concomitant medications will be recorded on the appropriate CRF and clinic notes and study logs will be entered into the subject's folder as source documents.
- A repeat prostate biopsy will be performed (12 core biopsy) and tissue / slides sent for assessment by Oncotype DX Prostate Cancer Test.
- Finally LUTS score will be assessed using the AUA BPH Symptom Score Questionnaire and all patients will complete the UCLA QoL questionnaire..
- Remaining study medication will be collected, counted, and appropriately stored while awaiting destruction.

Post-intervention Follow-up Period

Subjects will be contacted by telephone 7+/-3 days after discontinuing study agent to capture any signs and symptoms occurring since stopping the study drug and changes to concomitant medications. The subject is considered off study after the repeat biopsy, other end-of-intervention procedures, and final telephone contact are completed.

METHODS FOR CLINICAL PROCEDURES

Prostate Biopsy

Prostate tissue will be obtained and evaluated by a pathologist affiliated with the UHCC. Representative slides from the initial biopsy and from the biopsies obtained after treatment are required for analysis. At least eight (8) core biopsies will be obtained. Formalin-fixed paraffin-embedded prostate biopsy specimens from all patients included in this study will be performed at each site, where original slides will be stained with hematoxylin and eosin (H & E). The H&E stained sections will be evaluated by light microscopy for presence of prostate cancer by a pathologist with genitourinary experiences. Then if not previously performed, the biopsy paraffin blocks will be sent to Genomic Health to undergo Oncotype DX Prostate Cancer Test.

Blood Draw

Non-fasting blood samples will be drawn following standard institutional procedures. The amount of blood to be collected and the types of tubes is listed under section BLOOD COLLECTION SCHEDULE AND PURPOSE.

Anthropometric Measurements

Anthropometric measurements such as participant's height and weight will be performed at screening/pre-enrollment and post-intervention.

Page 24 of 38

Collection of AE and Concomitant Medications Information

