The primary efficacy endpoint is evaluation of the Genomic Prostate Score (GPS) after intervention with Noni extract. All subjects who meet eligibility criteria, have taken at least one dose of study medication, and have a post-treatment biopsy will be considered

evaluable for the primary efficacy endpoint. Tissue from prostate biopsies will be evaluated by a pathologist affiliated with the UHCC at screening and post-intervention with study agent. Representative slides from the diagnostic biopsy (at least 8 cores) and from biopsy specimens at 12 months post-intervention (at least 8 cores) are required for analysis. Biopsies will be obtained, and formalin-fixed. Paraffin-embedded prostate biopsy specimens from all patients included in this study will be prepared at each site, where original slides will be stained with H&E. Then biopsy samples will be shipped to Genomic Health to undergo Oncotype DX Prostate Cancer Test with the assessment of Genomic Prostate Score (GPS). The H&E-stained sections will be evaluated by light microscopy for presence of cancer, extent of cancer, grade of cancer by a centralized pathologist affiliated with UHCC, using uniform established standards.

Progression of Disease

PSA progression:

a) PSA doubling time (DT) < 2 years, based on at least 3 separate measurements over a minimum of 6 months

Histological progression:

- a) > 3 cores positive for prostate cancer;
- b) Gleason pattern predominant 4 or higher (i.e. Gleason 7 (4+3) or higher) in the rebiopsy specimen of the prostate performed at 12 months as per protocol

Clinical progression:

- a) more than twice increase in the product of the maximum perpendicular diameters of the primary lesion as measured radiographically
- b) local progression of prostate cancer requiring transurethral resection of the prostate
- c) development of ureteric obstruction
- d) radiological and/or clinical evidence of distant metastasis

Secondary Endpoints

The effects of Noni extract on serum PSA during the course of the study will be noted.

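### The positive-core progression criterion has no baseline reference, so a low risk man who enters with 4 or more positive cores can be counted as progressed with unchanged disease

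*Combined protocol and SAP*

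**What the plan says.** Under Criteria for Evaluation and Endpoint Definition, the Progression of Disease section gives two histological criteria. The first is "> 3 cores positive for prostate cancer". The second is predominant Gleason pattern 4 or higher at rebiopsy. The first is an absolute count and does not mention the diagnostic biopsy.

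Inclusion criterion 1 defines two entry groups. Very low risk includes a core limit: "fewer than 3 positive biopsy cores ≤ 50% cancer in any core". Low risk does not: "low risk (10% risk of disease relapse after primary treatment, criteria; cT1-2a, Gleason ≤6, PSA < 10 ng/mL) prostate cancer". Screening Visit Evaluation adds only a minimum: "prostate cancer must be present in at least one of 8 cores from the diagnostic biopsy". The Initial Assessment Form in Appendix C sets no maximum either.

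The number of cores is not fixed. The diagnostic biopsy needs at least 8. For the rebiopsy, Evaluations at Completion of Study Intervention says "A repeat prostate biopsy will be performed (12 core biopsy", while Prostate Biopsy, Primary Endpoint and Prostate Cancer Pathology all accept at least 8.

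On the role of progression, the synopsis lists "Incidence of tumor progression after 12 months of intervention with Noni extract" among the primary efficacy endpoints, and Objectives makes the one-year rate a primary objective. The Primary Endpoint section says instead: "The primary efficacy endpoint is evaluation of the Genomic Prostate Score (GPS) after intervention with Noni extract". Study Design/Endpoints agrees with that and puts progression among the other endpoints.

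**The concern.** Progression should mean change. The neighbouring criteria do imply change: predominant pattern 4 is new in a man who entered with Gleason 6 or lower, the radiographic criterion is an increase in lesion size, and PSA doubling time is a rate. The core count alone can be met by disease that was already there at entry.

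At stake is the one-year progression rate. The trial has a single arm, so the reported rate is the whole result for this objective, and no control group would show the same error.

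**Working it through.** **Entry limits against the progression rule**

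| Group | Positive cores allowed at entry | Can already meet the criterion (4 or more)? |
|---|---|---|
| Very low risk | 1 to 2 | No |
| Low risk | 1 or more, no maximum | Yes |

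Oncotype DX confirmation is also required, but nothing in the documents says that it limits the number of positive cores. No section excludes men who meet the criterion at baseline or requires a rise in the count.

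**The plan's own figure.** The plan gives no figure for progression. Its only design calculation concerns gene expression: 3.94 × (1.960 + 0.842)² / 1 = 30.9, against the stated 30. It is close, and it has no bearing on this point beyond supplying N = 30.

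**Weight of one man.** 1/30 = 3.3 percentage points. If core counts simply repeat at rebiopsy, 1, 3 or 6 such men add 1/30, 3/30 or 6/30, that is 3.3, 10 or 20 points. The numbers 1, 3 and 6 are assumptions. The net shift is smaller if some of these men also meet another progression criterion.

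**Allowing for resampling.** Assume unchanged disease, the sign as printed, independent cores, and a per-core probability p equal to the entry fraction. Then X ~ Binomial(n, p), and the criterion is met when X ≥ 4. For p = 4/12 and n = 12: 1 − (0.0077 + 0.0462 + 0.1272 + 0.2120) = 0.607.

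| Entry | 12-core rebiopsy | 8-core rebiopsy |
|---|---|---|
| 4/12 | 61% | 26% |
| 5/12 | 81% | 44% |
| 6/12 | 93% | 64% |

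If cores within a man are correlated (beta-binomial, assumed correlation 0.2), the 12-core values are 51%, 64% and 76%.

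Expected inflation is m × P / 30 for m such men. With independent cores and P taken from 4/12 to 6/12:

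| m (assumed) | 12-core rebiopsy | 8-core rebiopsy |
|---|---|---|
| 1 | 2.0 to 3.1 points | 0.9 to 2.1 points |
| 3 | 6.1 to 9.3 points | 2.6 to 6.4 points |
| 6 | 12.1 to 18.5 points | 5.2 to 12.7 points |

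**Unequal core numbers.** If 8 cores are taken at diagnosis and 12 at rebiopsy, an unchanged man at 2/8 reaches 4 or more of 12 with probability 35%, and one at 3/8 with probability 72%. With 12 cores at both biopsies, unchanged men at 1, 2 or 3 of 12 do so with probability 1%, 12.5% or 35%.

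**The case against.** The strongest reply is that little depends on this rate. The endpoint sections name GPS as primary, progression has no stated test, threshold or interval, and the core count is one of several components. Nothing shows that any man will actually enter with 4 or more positive cores. All of this stands and limits the weight of the point. It does not close the gap, because the rate is still a primary objective and the rule as written can count a man wrongly.

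The printed sign may also have lost an equals bar. Elsewhere the text shows bare signs where a parallel section has the or-equal form, for example age 55 and Gleason 6. If the threshold were 3 or more, the gap would remain but the probabilities would change: an unchanged man at 3/12 would meet it on 12 cores with probability 61%.

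Four stronger readings are tempting, and the documents do not support them:

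- A reader might infer that the trial's main conclusion is compromised. No planned decision rests on progression.
- A reader might take the resampling figures as upper bounds on the inflation. They are not: repeated counts give 3.3, 10 or 20 points for 1, 3 or 6 men, and entry above 6 of 12 also exceeds them.
- A reader might conclude that very low risk men are untouched. They cannot meet the criterion at entry, but unequal core numbers can still carry them over it by chance.
- A reader might infer that early rebiopsies fall outside the histological endpoint, because the grade criterion names the 12-month biopsy. Study Design/Endpoints largely covers this by using an earlier indicated biopsy for endpoint measurement.

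**Conclusion.** The concern holds as a gap in definition, and it should be fixed before the progression rate is reported. A low risk man with 4 or more positive cores is eligible and already meets the core criterion, and no section prevents him from being counted as progressed with unchanged disease.

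The total size cannot be derived, because the number of such men is not given. Each adds up to 3.3 points to a rate over 30 men. The probabilities above rest on unchanged disease, a constant per-core probability and the sign as printed. They fall markedly with an 8-core rebiopsy and moderately with correlated cores. The existence of the gap depends on none of these assumptions.

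**What to change.** For the analysis of the progression rate only:

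1. Confirm the threshold sign. State that the core criterion counts as progression only in men who did not already meet it at the diagnostic biopsy. Report the core component with men at or below the threshold at entry as its denominator.
2. Show the overall progression rate twice: as written, and with the core criterion not applied to men already above the threshold at entry. State that the second version misses true core progression in those men and so leans low. It should not stand alone as the replacement rate.
3. Record and report positive cores over cores taken, at both biopsies, for every man.

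The cost is a few sentences, one small table and a smaller denominator for the core component. The slides are already to be "evaluated by light microscopy for presence of cancer, extent of cancer, grade of cancer by a centralized pathologist affiliated with UHCC" at both time points, but extent is not stated to be a core count, so the counts need to be recorded explicitly. Chance resampling remains in all men; item 3 makes it visible but does not remove it.

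Progression also appears in the rules for treatment duration (Dose Regimen and Dose Groups), discontinuation (Rules for Dose Suspension and Discontinuation), Replacement and Off Study Criteria. The sponsor must keep the analysis definition separate from these or reconcile the sections. No clinical rule is proposed here.

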The incidence and severity of AEs occurring during intervention will be noted. All AEs that are reported by the subject, detected during a visit, physical examination, or laboratory work-up will be recorded in the participant's medical record and recorded on the CRF. All AEs that occur after study enrollment will be recorded on the AE CRF whether or not related to study agent. The following information will be captured for each AE: date reported; CTCAE Term (v 4.0); onset and resolution date; severity grade; attribution to study agent; whether or not the event was reported as an SAE; action taken; whether or not the subject dropped due to the AE; outcome; and comments.

Treatment related changes in angiogenesis (CD34), proliferation (Ki-67) and apoptosis (TUNEL) will be reported comparing initial diagnostic prostate biopsy and 12 month prostate biopsy provided sufficient tissue is available.

QoL and LUTS will be noted during the course of the study.

OFF DRUG CRITERIA

Participants may stop taking study agent for the following reasons:

- after completing the protocol-prescribed intervention
- at the discretion of the investigator
- AE or SAE requiring dose interruption
- inadequate agent supply
- noncompliance with study requirements
- medical contraindication

Off Study Criteria

If the subject never took study medication (e.g., does not meet eligibility criteria or withdraws consent prior to enrollment) the only activity required to remove the subject from the study is to complete the Off Study CRF. If the subject was enrolled and received study medication, post-intervention procedures according to the schedule of events should be completed to the extent possible.

Off-study criteria include:

- not meeting enrollment (eligibility) criteria
- the protocol intervention and any protocol-required follow-up period is completed
- experiencing an AE or SAE
- lost to follow-up
- taking a concomitant medication
- medical contraindication prohibiting further study participation
- discovery of a pre-existing condition not observed at baseline eligibility
- withdrawal of consent
- disease progression
- protocol non-compliance (i.e., visit schedule, dose administration, etc.)
- at the discretion of the investigator
- death

Study Termination

The study sponsor has the right to discontinue the study at any time.

SPECIMEN MANAGEMENT

Laboratories

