Clinical records for all participants, including CRFs, all source documentation (containing evidence to study eligibility, history and physical findings, laboratory data, results of consultations, etc.), as well as IRB records and other regulatory documentation will be retained by the each site investigator in a secure storage facility in compliance with HIPAA, OHRP, FDA regulations, and ICH requirements unless the standard at the site is more stringent for a minimum of two years. The sponsor will be notified prior to the planned destruction of any materials. The records should be accessible for inspection and copying by authorized persons of the Food and Drug Administration.

STATISTICAL CONSIDERATIONS

Sample Size

A number of methods have been developed to extract useful and robust information from genomic data sets. However, attention also has to be paid to the experimental design before the investigator completes the experiment. One of the principal limitations of previous molecular profiling studies is the relatively low numbers of samples analyzed. We needed to estimate the sample size requirements necessary to satisfy a specified false discovery rate and power given various biological and experimental variations. We estimated variance based on previous biomarker work. Sample size for this study was estimated according to equation

$$n = \frac{\sigma^2 (Z_{1-\alpha/2} + Z_{1-\beta})}{(\mu_1 - \mu_0)^2}$$

 $n = \frac{\sigma^2 (Z_{1-\alpha/2} + Z_{1-\beta})^2}{(\mu_1 - \mu_0)^2}$ where σ^2 is the variance of the gene expression, $Z_{1-\alpha/2}$, $Z_{1-\beta}$ are the $(1-\alpha/2)$ th, $(1-\beta)$ th quantile of the standard normal distribution respectively, with α being the type I error and β being the type II error. All signal values were log2

transformed. Variance was calculated for each protein. The 90th percentile variance value (3.94) was chosen be the σ^2 in equation. In order to detect a 2-fold change in the expression level, $(\mu_1 - \mu_0)^2$ in equation will be 1. We used 0.05 as the significance level. The estimated sample size is 30 for 80% power. Each patient will have 2 sets of genomic data (baseline and 12 months) collected over the course of the study to monitor a unique genomic signature associated with Noni extract in very low risk or low risk prostate cancer. The accrual rate is expected to be approximately 1 to 2 patients / month. Thus, it is expected to take about 15-30 months to accrue the 30 patients.

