Study Design/Endpoints

The proposed clinical study is a Phase II, single arm, open label trial in men > 55 years of age with biopsy proven (minimum of 8 cores) very low risk or low risk prostate cancer (confirmed by Oncotype DX Prostate Cancer Test); a total of 30 men will be enrolled. Subjects will receive Noni capsules (6,000 mg/day) for 12 months. After the planned 12-

month intervention is complete (or if a biopsy is indicated earlier), a repeat prostate biopsy will be performed for post-intervention endpoint measurements. The primary endpoint of the study is a comparison of the Genomic Prostate Score (GPS) after treatment with Noni extract. Furthermore, pelvic MRI with contrast will be performed and the size of any lesion calculated. Radiologic report of the MRI should be collected as it is a source document. Other endpoints include: investigating progression of prostate cancer after treatment with Noni extract, investigating modulation of serum PSA after treatment with Noni extract, reporting the tolerability of Noni extract in men with very low risk and low risk prostate cancer, investigating key molecular changes associated with angiogenesis, proliferation or apoptosis and reporting quality of life elements.

ETHICAL AND REGULATORY CONSIDERATIONS

This study is to be conducted according to US and international standards of Good Clinical Practice (FDA Title 21 part 312 and International Conference on Harmonization guidelines), applicable government regulations and Institutional research policies and procedures.

Informed Consent

All potential study participants will be given a copy of the IRB-approved Informed Consent to review. The investigator or qualified study staff will explain all aspects of the study in lay language and answer all questions regarding the study. If the participant decides to participate in the study, he will be asked to sign the Informed Consent document. The subject is considered enrolled in the study from the time the informed consent document is signed. Any and all AEs and concomitant medication taken by the study participant must be captured up to the time of termination from the study. The study agent(s) will not be released to a participant who has not signed the Informed Consent document. Subjects who refuse to participate or who withdraw from the study will be treated without prejudice.

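### Before-after biopsy and PSA differences in a single arm are labelled as Noni effects, which this design cannot establish; they should be reported as descriptive change.

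*Combined protocol and SAP*

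**What the plan says.** Study Design/Endpoints, under Statistical Considerations, sets the design: "The proposed clinical study is a Phase II, single arm, open label trial". No untreated group, historical series, expected change without treatment or repeat-biopsy variability appears anywhere in the document.

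Three places attach a causal label to a within-patient difference:

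- **Tissue markers** (Criteria for Evaluation and Endpoint Definition, Secondary Endpoints): "Treatment related changes in angiogenesis (CD34), proliferation (Ki-67) and apoptosis (TUNEL) will be reported comparing initial diagnostic prostate biopsy and 12 month prostate biopsy", where enough tissue is available.
- **Gene expression** (synopsis, Endpoints, first primary efficacy item): "Induction of favorable gene expression changes on Oncotype Dx Prostate Cancer Test after 12 months of intervention with Noni extract".
- **PSA** (Secondary Endpoints): "The effects of Noni extract on serum PSA during the course of the study will be noted".

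Elsewhere the same primary endpoint is put neutrally. Primary Endpoint describes evaluating the Genomic Prostate Score (GPS) after the intervention, and Study Design/Endpoints describes comparing GPS after treatment.

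**The concern.** A before-after difference in one arm estimates change over the interval. It estimates a drug effect only if nothing else would have moved the measurement, and the plan neither argues that nor supplies a reference from which it could be judged. The document itself shows several other routes to a difference: the time elapsed, different tissue sampled at each biopsy, diagnostic biopsies that may come from outside the consortium, and a variable gap between the biopsies, part of which precedes any drug.

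The label is nonetheless fixed in advance. Followed as written, the plan reports whatever change is seen in CD34, Ki-67 and TUNEL as related to treatment, and a favorable expression change as induced. The Clinical Experience section calls the study a confirmatory phase II trial, so such wording could carry weight in the report. At stake is a primary efficacy statement that the data cannot support.

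**Working it through.** **1. What the sample size tests.** Sample Size (Statistical Considerations) gives variance 3.94 on the log2 scale, a 2-fold change (difference 1), significance level 0.05 with the 1−α/2 quantile (so two-sided), and 80% power.

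n = σ²(z₀.₉₇₅ + z₀.₈₀)² / (μ₁ − μ₀)² = 3.94 × (1.960 + 0.842)² / 1² = 30.9

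The plan states 30, so the figure reproduces to within rounding. The two-group version with the same inputs would need 62 per arm. The plan is therefore sized for a one-sample test of mean change against zero, and its null hypothesis is no change, which is not the same as no drug effect.

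**2. Non-drug sources of difference shown in the document.**

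| Source | Where | What it allows |
|---|---|---|
| Interval | Recruitment Plan: diagnosis within 12 months. Appendix C: biopsy within 6 months | With repeat biopsy at month 12, pairs about 12–24 or 12–18 months apart, partly before any drug. An early repeat biopsy shortens this. |
| Sampling | Screening and Primary Endpoint: at least 8 cores at diagnosis. Schedule of Events: 12 cores at month 12, although Primary Endpoint says at least 8 | Different tissue, possibly different core numbers |
| Origin and assay timing | Laboratories: diagnostic biopsy may have been analyzed outside the consortium. Prostate Biopsy: Oncotype DX run only if not already done | Paired specimens collected or assayed under different conditions |
| Selection | Inclusion Criteria: low grade and risk group, confirmed by Oncotype DX | Regression upward in the second GPS or grade, which is unfavorable. CD34, Ki-67 and TUNEL are not entry criteria. |

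The document gives no size for any of these.

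**3. Illustration of scale.** Assumptions, none of them stated in the plan: a two-sided paired t-test at 0.05, 30 complete pairs, 3.94 as the variance of the paired difference (the plan does not say whether it is that or the variance of a single measurement), zero drug effect, and a mean drift of d SD.

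SD = √3.94 = 1.985 log2 units. Fold change = 2^(1.985d). Noncentrality = d√30. Critical value t₀.₉₇₅,₂₉ = 2.045.

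| d (SD) | log2 drift | Fold | Noncentrality | P(significant) |
|---|---|---|---|---|
| 0 | 0 | 1.00 | 0 | 5.0% |
| 0.1 | 0.198 | 1.15 | 0.548 | 8.3% |
| 0.2 | 0.397 | 1.32 | 1.095 | 18.5% |
| 0.3 | 0.595 | 1.51 | 1.643 | 35.5% |

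These are two-sided rates. The endpoint counts only favorable change, so they bear on it only if the drift runs the favorable way; in that case nearly all the rejections fall on that side (7.6%, 18.4% and 35.5%). If the drift is unfavorable, the chance of a significant favorable result falls below 2.5%.

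I stop at 0.3 SD. A drift of 0.5 SD is 0.99 log2 units, or about 2-fold, which is the whole effect the trial is sized to detect. The 75% rejection rate there is essentially the trial's own t-test power (76.0% at a 2-fold change).

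**The case against.** The strongest reply is that no inferential claim is planned. No test is named for CD34, Ki-67 or TUNEL, the Objectives describe that work as exploratory, and 0.05 appears only in the sample-size calculation, which concerns gene expression. No rule links a p-value to a conclusion about Noni. This stands. The rates above illustrate a test inferred from the sample-size formula; they are not the error rate of a stated decision rule.

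A reader might also infer that drift in any direction would be credited to the drug, or that a favorable shift is to be expected without it. The document supports neither. The synopsis endpoint counts only favorable change, and selection on a low first GPS or grade works against it. Sampling different tissue mainly adds variance. Comparability is partly protected: a centralized pathologist reads both biopsies to uniform standards, one company runs GPS, and one laboratory does the stains. What remains is that a mean shift cannot be excluded or sized.

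The wording is also uneven. GPS is described neutrally in two places, and the Sample Size phrase "to monitor a unique genomic signature associated with Noni extract in very low risk or low risk prostate cancer" is associational, so I do not count it as a causal claim. The planned correlation of plasma scopoletin with molecular changes (Adherence/Compliance) bears on attribution, but it has no stated method and cannot estimate change without the drug.

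Finally, a single-arm phase II trial is a legitimate design. That is accepted: the fault lies in the labels, given without a reference or caveat.

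**Conclusion.** The point holds as one of attribution. Three passages label uncontrolled before-after differences as effects of Noni, and nothing in the plan allows a drug effect to be separated from change over time, sampling, or differences in biopsy origin and interval.

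The size of any such drift is unknown. Under the stated assumptions, a no-drug drift of 0.1 to 0.3 SD, about 1.15- to 1.5-fold, would reach significance in 8% to 36% of trials. It should not be read as a demonstrated inflation of a false-positive rate: the plan specifies no test for the tissue markers, the drift values are assumed, and the one direction the document hints at is unfavorable. Nor is the sample size at fault, since 30 reproduces for a test of change against zero.

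The change should be made: it alters what may be concluded, at almost no cost.

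**What to change.** - **Synopsis, Endpoints:** replace the 'induction' wording with change from the diagnostic biopsy in gene expression on the Oncotype DX test.
- **Secondary Endpoints, tissue markers:** replace 'treatment related changes' with change from the diagnostic biopsy.
- **Secondary Endpoints, PSA:** replace 'effects of Noni extract' with change from baseline in serum PSA.
- **Statistical Considerations:** add a statement that these paired differences will be reported with 95% confidence intervals, are descriptive, and will not by themselves be attributed to Noni.

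This brings the three passages into line with the neutral GPS wording already in Study Design/Endpoints. Sample size, visits, tissue handling and patient care are unchanged. The cost is that the permitted conclusion becomes less favorable: the trial may report that a measurement changed, but not that Noni changed it.
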